**13. Body location affected**

hand/finger     calf and knee     hip and thigh     trunk     foot and ankle joints  
 shoulder     head     internal organs     upper arm and forearm

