## **2. Methods**

A survey (as outlined below) of mountain biking related injuries will be conducted on the participants of the Swiss Epic mountain bike event in 2017 held in Valais. The retrospective questionnaire is designed in accordance with existing literature ((Gaulrapp et al., 2001; Lareau and McGinnis, 2011), will include 25 questions and will be translated into English, French, Italian, Spanish and German. The participants will be asked to tick the most appropriate answer. The questionnaire aims to assess the athletes' 1) basic demographics, riding level and years of experience, 2) number of races per year and mean hours of training per week, 3) number and kind of suffered injuries related to mountain biking and medical treatment requirement, 4) and amount and kind of protective gear items.

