## Mountain biking Injury Questionnaire

*Thank you for agreeing to take part in this important questionnaire about mountain biking injuries. The information we can obtain from this survey may help to improve the knowledge about injury prevalence in mountain biking. With this knowledge, it may be possible to improve safety in future and prevent injury.*

*Be assured that all answers you provide will be kept in the strictest confidentiality. This survey is anonymous. Do not write your name on the survey.*

*Please tick only the most correct answer.*

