**11. Mechanism of injury**

loss of control       loss of traction       collision with object       collision with rider       mechanical problem  
 unknown       other \_\_\_\_\_

**12. Severity of injury** (if more than one injury occurred, choose the most severe one)

no medical treatment needed     self-administered medical treatment     MD administrated medical treatment     Medical treatment in ER     Overnight hospitalization

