**14. Type of injury**

bone fractures     joint injuries     skin and soft tissue injuries     concussion

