**20. If you experience NOT injury related pain, where is it located?**

knee     neck     lower back     hip     buttocks

other \_\_\_\_\_

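### Items 13 and 14 have no 'other' line, no neck site and no type for an organ injury, so some injuries must be misfiled or left blank

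*Combined protocol and SAP*

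**What the plan says.** Section 2 (Methods) lists four things the questionnaire is meant to assess. The third is "number and kind of suffered injuries related to mountain biking and medical treatment requirement". Section 3 (Statistical analysis plan) says that descriptive results will be given as means with standard deviations and as relative frequencies. It has no rule for blank or unclassifiable answers.

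The kind of injury is recorded mainly by two items of the Mountain biking Injury Questionnaire:

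- "13. Body location affected" offers nine fixed sites: hand or finger, calf/knee, hip/thigh, trunk, foot/ankle, shoulder, head, upper arm/forearm, and "internal organs".
- "14. Type of injury" offers four fixed types: fracture, joint injury, skin or soft-tissue injury, and concussion.

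Neither item has an 'other' or 'unknown' option. The introduction to the form instructs: "Please tick only the most correct answer". Other items are more open. Item 8 (protective gear), item 11 ("11. Mechanism of injury"), item 20 and item 21 (treatment of soreness) each end with a free-text 'other', and item 11 also has 'unknown'. Item 20, "If you experience NOT injury related pain, where is it located", names knee, neck, lower back, hip and buttocks before its 'other' line.

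**The concern.** A closed single-answer list works only if every case has a class. Here two kinds of case do not. A rider with a neck injury finds no neck option in item 13. A rider who ticks the organ site in item 13 finds no clearly fitting type in item 14. Each must choose an ill-fitting class or skip the item, and different riders may choose differently.

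The study's aim is descriptive, so the frequencies of site and type are results in their own right, and the form says that they should help to prevent injury. Misfiling is a bias and does not shrink with more respondents. It is also hard to undo: the survey is anonymous, so riders cannot be asked again, and these two items hold no free text to recode. If site or type were used as a predictor in the planned logistic regressions, the misclassification would carry over to them.

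**Working it through.** The documents state no sample size, injury distribution or expected frequency for these items, so there is no figure of the plan to reproduce. The check compares the lists and then illustrates the effect on a percentage.

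**Step 1. Sites named in item 20 against the sites in item 13**

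| Item 20 | Match in item 13 |
|---|---|
| knee | calf/knee, by name |
| hip | hip/thigh, by name |
| lower back | none by name; trunk covers it |
| buttocks | none by name; hip/thigh covers it |
| neck | none by name; head, trunk and shoulder all adjoin it |

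The neck is the one clear gap.

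**Step 2. Sites in item 13 against types in item 14.** Eight of the nine sites can take at least the skin or soft-tissue type. The ninth, "internal organs", has no type written for it: an organ injury is not a fracture, a joint injury or a concussion, and the skin-and-soft-tissue class would have to be stretched to hold it.

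**Step 3. Escape options.** 'Other' is present in items 8, 11, 20 and 21, and absent from items 13 and 14.

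**Step 4. Illustration of size.** Let *m* be the share of injuries without a fitting class and *p* the true share of some existing class. Both values below are assumptions and neither is in the documents: *p* = 10%, *m* = 2% or 5%.

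- Left blank and dropped from the denominator, the class reads *p*/(1 − *m*).
  - *m* = 2%: 0.10/0.98 = 10.2%
  - *m* = 5%: 0.10/0.95 = 10.5%
- All forced into that one class, it reads *p* + *m*.
  - *m* = 2%: 10% + 2% = 12%
  - *m* = 5%: 10% + 5% = 15%

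The second pair is the extreme for a single class. If riders spread over several classes, each is inflated by less. In every case the missing class itself is reported as zero instead of *m*.

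**The case against.** The best defence is that the lists are coarse rather than wrong. Riders are asked for the best-fitting answer, and a broad region is a legitimate class. That stands for most sites. A reader might infer that spine, lower back and facial injuries also have no home. They do: lower back and most spine injuries fall under trunk, and the face under head. Wanting separate boxes for them is a preference for finer detail. The defence does not cover the neck, which lies between classes.

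A reader might also infer that item 14 omits an injury type named elsewhere on the form, or that organ injuries are lost. Neither follows. No item names organ injury as a type; the gap is inferred from the site offered in item 13. That site answer still captures the organ injury itself, so only its type is affected.

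Item 20 is modest evidence. It asks about pain unrelated to injury, so it shows that the neck was recognised as a distinct site, not that neck injuries were expected or common.

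Importance is limited too. Section 3 names no test on site or type. Its stated targets are injury prevalence, severe versus mild injury, and differences between elites and amateurs. A reader might fear that the most serious injuries drop out of the severity analysis, but item 12 is answered separately and has its own complete scale.

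Finally, Section 2 says that the questionnaire follows existing literature. Whether these lists mirror an earlier instrument cannot be checked from the documents. Keeping the existing options unchanged limits any loss of comparability.

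**Conclusion.** The point holds in a narrow form. Items 13 and 14 lack the 'other' line used in four other items, item 13 has no place for the neck, and item 14 has no clear type for the organ site that item 13 offers. Neck injuries, and the type of organ injuries, will be misfiled or blank, which distorts the location and type frequencies.

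How many injuries are affected is unknown. A reader might want to attach a substantial percentage, but the documents support none. The illustrated shift, from 10% to between 10.2% and 15%, rests wholly on an assumed 2–5% of unclassifiable injuries and on whether riders skip the item or all tick the same class. Severity results from item 12 are untouched. This is a minor defect, worth correcting because the correction is cheap.

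**What to change.** Change the two items before the form is issued:

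- Item 13: add neck and a free-text 'other'.
- Item 14: add internal organ injury and a free-text 'other'.
- Make the same change in all five language versions, and leave the existing options as they are.
- In Section 3, state that the number of blank answers to items 13 and 14 will be reported beside the relative frequencies.

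The cost is a few tick boxes, their translation, and a little free-text coding in five languages, which four other items already require.

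If forms have already been collected, the blanks can still be counted and the limit stated. Riders who ticked the organ site can be shown separately in the type table. Neck injuries ticked under another site cannot be recovered.

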**14. Type of injury**

bone fractures     joint injuries     skin and soft tissue injuries     concussion

**15. Days return to sports**

\_\_\_\_\_ days

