## **3. Statistical analysis plan**

Data analyses will be performed using the Statistical Package for Social Sciences (SPSS), version 24.0 (IBM Corporation, Armonk, NY, USA).

Descriptive statistics [means  $\pm$  standard deviations (SD) and relative frequencies (%)] will be retrieved. Pearson correlations will be used to assess correlations between the outcome variables. Chi-squared tests will be applied to determine group differences of injury prevalence and the occurrence of severe, respectively mild injury events. Multivariate logistic regressions will be performed to evaluate predictive factors among the outcome variables (independent variables) of severe injury events (dependent variable; no severe injury = 0 versus severe injury = 1) in elites and amateurs separately. Independent samples t-tests will be used to evaluate mean group differences in demographics, and training and injury related variables between the elite and the amateur mountain bikers. P-values  $< 0.05$  will be considered as statistically significant. According to Cohen (1992), effect sizes will be calculated for the correlation analyses and defined as follows;  $r = 0.20$  small,  $r = 0.50$  medium,  $r = 0.80$  strong.

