**9. Number of injuries obtained during mountain biking**

\_\_\_\_\_

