**16. Days return to work**

\_\_\_\_\_ days

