**17. Did you fully recover from the injury?**

full recovery     partial recovery

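### Item 15 (days to return to sports) fixes neither the level of return nor the injury meant, so its group means may have no single meaning and an elite-amateur comparison of it could be biased in an unknown direction

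*Combined protocol and SAP*

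**What the plan says.** The combined protocol and SAP measures sporting time lost with a single questionnaire item, number 15: "Days return to sports", answered as a number of days. Item 16, "Days return to work", has the same form.

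Other injury items are more specific in places. Item 9 asks for "Number of injuries obtained during mountain biking". Item 10 asks how long ago the most recent injury was. Item 12 asks about severity and tells riders with several injuries to choose the worst. Item 17 asks "Did you fully recover from the injury", with full or partial recovery as the answers. The general instruction, "Please tick only the most correct answer", governs ticking and defines no terms.

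Section 3 (Statistical analysis plan) sets independent samples t-tests for "mean group differences in demographics, and training and injury related variables between the elite and the amateur mountain bikers". P-values below 0.05 "will be considered as statistically significant". Item 15 is not named there. As a numeric injury item it falls within that description by inference.

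**The concern.** A rider answering item 15 has to decide three things that the form leaves open:

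- **Level of return.** The first ride, usual training and racing again can be well apart in time.
- **Sport.** The word used is the general one, not mountain biking.
- **Index injury.** Items 10 and 12 point to different injuries for anyone hurt more than once, and item 15 repeats neither.

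There is also no answer for a rider who has not yet returned.

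If riders settle these points differently, the mean and SD of item 15 describe a mixture of quantities. If elites and amateurs also settle them differently, a difference in how the question was read would appear as a difference in recovery time. The form is anonymous and nothing on it records the reading chosen, so neither problem can be corrected after collection.

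**Working it through.** **1. Is the milestone defined anywhere?** Section 2 (Methods) lists the injury content as number and kind of injuries and the need for medical treatment; return to sport is not mentioned. The questionnaire's introduction defines no terms. Item 16 concerns work and is equally undefined. Item 17 separates full from partial recovery but is not tied to the day given in item 15. Item 18 concerns pain. So no definition of the level of return exists in the documents, and the injury referred to is not restated.

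**2. Is there a figure to reproduce?** No. The documents give no sample size, SD, expected days lost or effect size. Everything below rests on assumed inputs and only illustrates scale.

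**3. Relative difference in means.** Let true recovery be identical in both groups. Let *r* be the time to first activity divided by the time to riding again, and *w* the share of a group that reports first activity. Relative to everyone reporting the ride:

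group mean = 1 − *w*(1 − *r*)

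Assumed: *r* = 0.3, 0.5 or 0.7; shares 0.7 v 0.3 (40 points apart) or 0.6 v 0.4 (20 points apart).

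| *r* | shares | lower mean | higher mean | ratio | lower group is below by |
|---|---|---|---|---|---|
| 0.3 | 0.7 v 0.3 | 1 − 0.7×0.7 = 0.51 | 1 − 0.3×0.7 = 0.79 | 0.646 | 35% |
| 0.3 | 0.6 v 0.4 | 0.58 | 0.72 | 0.806 | 19% |
| 0.5 | 0.7 v 0.3 | 0.65 | 0.85 | 0.765 | 24% |
| 0.5 | 0.6 v 0.4 | 0.70 | 0.80 | 0.875 | 12.5% |
| 0.7 | 0.7 v 0.3 | 0.79 | 0.91 | 0.868 | 13% |
| 0.7 | 0.6 v 0.4 | 0.82 | 0.88 | 0.932 | 7% |

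The percentages take the higher group as reference. Nothing in the documents says which group has the larger *w*, so either can be the lower one. With equal shares the ratio is 1 and the difference is zero.

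**4. The same in days, with the effect on the test.** Let two readings lie *g* days apart and let the shares using the later reading be *p*₁ and *p*₂:

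false difference = *g*(*p*₁ − *p*₂)

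variance = *s*² + *g*²[*p*₁(1 − *p*₁) + *p*₂(1 − *p*₂)]/2

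standard error = √(variance × 2/*n*)

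Assumed: *s* = 30 days within a reading; *g* = 7, 14 or 28; *n* = 50 to 200 injured riders per group; a two-sided 5% test by normal approximation (the plan does not state sidedness).

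- 50% v 50%: false difference 0 days; rejection rate 5%.
- 60% v 40%: 7×0.2 = 1.4, 14×0.2 = 2.8, 28×0.2 = 5.6 days; rejection rate 6% to 40%.
- 70% v 30%: 7×0.4 = 2.8, 14×0.4 = 5.6, 28×0.4 = 11.2 days; rejection rate 8% to 93%.

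**5. If the groups read the item alike.** With a 50/50 split in both, the mixture adds *g*²×0.25 to a variance of 900: 12.25 (1.4%) at *g* = 7, 49 (5.4%) at *g* = 14 and 196 (22%) at *g* = 28. The comparison is unbiased but somewhat noisier, and neither mean refers to a stated milestone.

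**The case against.** The strongest reply is that context supplies most of what is missing. The form is headed as a mountain biking injury questionnaire, is given to entrants at a mountain bike race, and names the sport in item 9. Items 6 and 7, on training hours and races, also leave the sport out, so item 15 follows the form's own shorthand. This stands: mountain biking is the natural reading of the word, and a swim or a home-trainer session is possible but less likely. The reply does not settle the level of return or which injury is meant.

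Item 15's role is also limited. Section 2 does not list time to return among what the questionnaire assesses, the only modelled dependent variable is severe injury, and the stated aim is descriptive. A reader might infer that days lost is a main measure of the effects of injury; the documents do not say so.

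A reader might also infer that riders do report different milestones, or that the wording makes elites look faster to recover. Neither is supported. The documents show undefined wording, not how riders read it. Elites might report early substitute training, which would shorten their figure, or take return to mean racing, which would lengthen it. Only the English form is available, so the wording in the other languages is unknown.

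**Conclusion.** The point holds as a minor measurement defect. Item 15 leaves the level of return and the index injury open and names the sport only through context; it also gives no answer for riders not yet back. No later analysis can repair this.

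The loss of a clear meaning follows if riders differ in their reading at all. Bias in the elite-amateur comparison needs more: the two groups must read the item in different proportions, and item 15 must be among the variables tested, which is an inference from the wording of section 3. The 7% to 35% range depends entirely on the assumed shares and ratios, has no fixed sign, and becomes zero when the groups read the item alike. It indicates possible scale and is not an estimate for this survey.

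**What to change.** Reword item 15 to one milestone, one sport and one index injury. For example: 'For the most severe injury (question 12): days from the injury until you first rode a mountain bike again (0 if no days missed; tick if not yet returned)'. Use the same wording in all five language versions. Another single milestone, such as full training, is equally acceptable if it is stated on the form.

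If forms have already been used, report the variable as self-defined time to return and qualify the elite-amateur comparison accordingly.

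The cost is one slightly longer line on the form and in the translations.

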**6. Estimated training hours per week in regard to the season**

Spring \_\_\_\_\_ h/Week      Summer \_\_\_\_\_ h/Week      Autumn \_\_\_\_\_ h/Week      Winter \_\_\_\_\_ h/Week

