**7. How many races per year**

\_\_\_\_\_

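### Open number lines for training hours and days lost do not ask for a 0, so a blank is ambiguous and Section 3 has no rule for it

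*Combined protocol and SAP*

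**What the plan says.** Item 15 ("Days return to sports") and item 16 ("Days return to work") each give one open line in days. Item 6 ("Estimated training hours per week in regard to the season") gives four open lines, one per season. None mentions 0, and none has a box for none or not applicable. Items 18 and 19, which are tick items, do offer a negative answer.

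The only general completion instruction, "Please tick only the most correct answer", concerns tick boxes. Item 9 ("Number of injuries obtained during mountain biking") is also an open line, and no skip follows it, so uninjured riders meet the injury items too. The lowest severity level in item 12 is "no medical treatment needed", so trivial injuries are within scope. The survey is anonymous.

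Section 2 lists "mean hours of training per week" among the things to be assessed. Section 3 plans means with standard deviations, and t-tests between elite and amateur riders on demographic, training and injury variables. It does not say whether a blank is dropped, coded as 0 or imputed, nor how four seasonal entries become one weekly mean.

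**The concern.** Asking for days until return presupposes an absence. A rider whose injury cost no day has nothing to return from and may leave the line empty. A rider who does not train in winter may likewise leave that season empty. Because the form is anonymous, nobody can be asked afterwards what a blank meant.

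Two outputs are at stake. Days lost is a direct measure of the effects of injury that Section 1 sets out to describe. If injuries without lost time fall out of the denominator, the mean describes mainly the injuries that cost time. Weekly training hours are a stated target of the questionnaire, and their value depends on what is done with an empty season.

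**Working it through.** The documents give no expected mean, sample size or blank rate, so there is no figure of the plan's own to reproduce. The calculation shows how far each way of handling blanks could move a mean. All rates and example values below are assumptions.

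**1. Days lost, blanks dropped.** Let z be the share of injured riders whose true answer is 0, and b the share of those who leave the line blank. Other non-response is taken as random. Dropping blank zeros leaves the total unchanged and shrinks the denominator to 1 − z·b, so observed mean / true mean = 1/(1 − z·b).

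| z | b | z·b | ratio |
|---|---|---|---|
| any | 0 | 0 | 1.00 |
| 0.2 | 0.1 | 0.02 | 1.02 |
| 0.4 | 0.1 | 0.04 | 1.04 |
| 0.2 | 0.5 | 0.10 | 1.11 |
| 0.4 | 0.5 | 0.20 | 1.25 |

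The same formula applies to the mean hours of any one season in item 6.

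**2. All blanks coded as 0.** If a share m of injured riders simply did not answer, at random, the ratio is 1 − m: 0.95, 0.90 and 0.80 at m = 5%, 10% and 20%. The bias is now downward.

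**3. Blanks that hide long absences.** Take a true mean of 10 days with 10% blank zeros. Dropping them gives 10/0.90 = 11.1. If a further 2% with 60-day absences also leave the line blank, the result is (10 − 0.02 × 60)/0.88 = 10.0. If 5% do, it is (10 − 0.05 × 60)/0.85 = 8.2. So even when blanks are dropped, the direction is not fixed.

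**4. Weekly training hours.** A rider's mean over filled seasons only is inflated by 4/(4 − k) when k zero seasons are blank: 1.33 for one, 2.00 for two. For example, a rider with 10, 12 and 8 h and a blank winter scores 30/3 = 10.0 instead of 30/4 = 7.5.

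For a group, suppose every rider trains 10, 12 and 8 h in the other seasons; 40% train 0 h in winter (mean 7.5) and 60% train 4 h (mean 34/4 = 8.5). The true group mean is 0.4 × 7.5 + 0.6 × 8.5 = 8.1. If half of the zero winters are blank:

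- averaging filled seasons: 0.2 × 10 + 0.2 × 7.5 + 0.6 × 8.5 = 8.6 (+6%);
- using only riders with all four seasons: (0.2 × 7.5 + 0.6 × 8.5)/0.8 = 8.25 (+1.9%).

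The choice of rule alone moves the result, and Section 3 makes no choice.

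**The case against.** The strongest reply is that nothing here is bound to go wrong. A rider can write 0 on any of these lines, so zero and not answered coincide only for those who leave a true zero blank. Section 3 does not say that blanks are dropped, and naming SPSS does not settle it, because what goes into the cell is decided at data entry. Many blanks at items 15 and 16 will come from riders never injured; leaving them out is right for a mean per injured rider, and item 9 identifies them if it is filled in. Item 12 also hints at which injuries cost no time. All of this stands, and it makes the upward bias conditional. It does not remove the ambiguity: item 9 is itself an open line, and untreated is not the same as no day lost.

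The offset in step 3 also stands as a possibility. It is less likely for item 15, because every respondent is taking part in the event and so is riding again, although item 17 allows for partial recovery.

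A reader might infer three stronger claims that the documents do not support:

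- *The means will be overstated.* Neither the handling rule nor any blank rate is given, and other handling reverses the direction.
- *The elite–amateur contrast is distorted.* That needs blank zeros to be more common at one level, and nothing in the documents shows this.
- *Item 7 ("How many races per year") has the same defect.* It is also an open line, but all respondents are race entrants, so a true zero is implausible and a blank there most likely means not answered.

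**Conclusion.** The point holds as a minor weakness of the form together with a missing rule in Section 3. Blanks at items 6, 15 and 16 cannot be reliably told apart from true zeros, and the affected variables feed planned means and t-tests.

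The upward bias in mean days lost arises only if true zeros are left blank, the blanks are dropped, and long absences are not also left blank. With 20–40% true zeros it is negligible if nearly all riders write 0, 2–4% if one in ten leaves a true zero blank, and 11–25% if half do. For weekly hours it also depends on how the seasons are combined. None of these rates can be checked against the documents.

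**What to change.** On the form:

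- Item 6: print *write 0 if none* at each season.
- After item 9: add *if 0 injuries, skip to item 19*. Without this, a prompt to write 0 would invite false zeros from uninjured riders at items 15 and 16.
- Item 15: reword to *Days of sport missed because of this injury (write 0 if none)*.
- Item 16: reword to *Days of work missed because of this injury (write 0 if none; tick if not working)*. Separate wordings keep sport and work distinct, and the box prevents false zeros from riders without a job.

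In Section 3:

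- Treat a written 0 as a value and a blank as missing.
- Restrict items 15 and 16 to injured riders.
- Compute mean weekly hours from riders with all four seasons filled. This loses some riders, but fewer once the form asks for 0, and it does not change the meaning of the mean from rider to rider.
- Report the number of blanks per item by riding level, with a sensitivity analysis coding blanks as 0. The two analyses bracket the truth if blanks are a mixture of zeros and random non-response, but not if they hide long absences.

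The cost is a few words in five language versions and a little extra analysis. If the forms are already fixed, the additions to Section 3 are still worth making.
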